#### **6.2.5 Pregnancy**

Any pregnancy that occurs during study participation must be reported to NOVARTIS. To ensure subject safety, each pregnancy must be reported to NOVARTIS within 2 weeks of learning of its occurrence. The pregnancy must be followed up to determine outcome (including premature termination) and status of mother and child. Pregnancy complications and elective terminations for medical reasons must be reported as an AE or SAE. Spontaneous abortions must be reported as an SAE.

Any SAE occurring in association with a pregnancy, brought to the investigator's attention after the subject has completed the study and considered by the investigator as possibly related to the investigational product, must be promptly reported to NOVARTIS. In addition, the investigator must attempt to collect pregnancy information on any female partners of male study subjects who become pregnant while the subject is enrolled in the study. Pregnancy information must be reported to NOVARTIS as described above.

### **6.3 Report of Adverse Events to the Institutional Review Board**

The principal Investigator is required to notify his/her Institutional Review Board (IRB) of a serious adverse event according to institutional policy.

### **6.4 Investigator Reporting to the FDA**

Serious adverse events (SAEs) that are **unlisted/unexpected, and at least possibly associated to the drug**, and that have not previously been reported in the Investigators brochure, or reference safety information document should be reported promptly to the Food and Drug Administration (FDA) by telephone or by fax. Fatal or life threatening SAEs that meet the criteria for reporting to the FDA must be reported to the FDA within 7 calendar days after awareness of the event. All other SAEs that meet the criteria for reporting to the FDA must be reported to the FDA within 15 calendar days after awareness of the event. A clear description of the suspected reaction should be provided along with an assessment as to whether the event is drug or disease related.

### **6.5 Adverse event updates/IND safety reports**

The supporters (NOVARTIS and Celgene Corporation) shall notify the Investigator via an IND Safety Report of the following information:

- Any AE associated with the use of drug in this study or in other studies that is both serious and unexpected.

---

- Any finding from tests in laboratory animals that suggests a significant risk for human subjects including reports of mutagenicity, teratogenicity, or carcinogenicity.

The Investigator shall notify his/her IRB/EC promptly of these new serious and unexpected AE(s) or significant risks to subjects.

The Investigator must keep copies of all AE information, including correspondence with the supporters and the IRB/EC, on file (see Section 11.4 for records retention information).

## **7 Response Criteria**

Baseline lesion assessments must occur within ≤ 28 days of protocol therapy initiation or as indicated in Section 2, Schedule of Study Assessments.

Efficacy assessments will be performed as delineated in Section 2, Schedule of Study Assessments Table.

Assessment for response will be made following the NCIWG 2008 CLL criteria for response (See Appendix F: NCIWG 2008 CLL Criteria for Response).

## **8 Protocol Amendments/Deviations**

### **8.1 Protocol amendments**

Any amendment to this protocol must be agreed to by the Principal Investigator and reviewed by Celgene Corporation and Novartis. Amendments should only be submitted to IRB/EC after consideration of Celgene Corporation and Novartis review. Written verification of IRB/EC approval will be obtained before any amendment is implemented.

## **8.2 Protocol deviations**

When an emergency occurs that requires a deviation from the protocol for a subject, a deviation will be made only for that subject. A decision will be made as soon as possible to determine whether or not the subject (for whom the deviation from protocol was effected) is to continue in the study. The subject's medical records will completely describe the deviation from the protocol and state the reasons for such deviation. In addition, the Investigator will notify the IRB/EC in writing of such deviation from protocol.

Non-emergency minor deviations from the protocol will be permitted with approval of the Principal Investigator.

# **9 Data Management**

## **9.1 Analyses and Reporting**

Data will be analyzed and reported after completion of treatment protocol. All subsequent data collected will be analyzed and reported in a follow-up clinical report.

## **9.2 Study auditing**

### **9.2.1 Investigator responsibilities**

Investigator responsibilities are set out in the ICH guideline for Good Clinical Practice (GCP) and in the US Code of Federal Regulations.

Investigators must enter study data onto CRFs or other data collection system. The Investigator will permit study-related audits by Celgene or its representatives, IRB/EC review, and regulatory inspection(s) (e.g., FDA, EMEA, TPP), providing direct access to the facilities where the study took place, to source documents, to CRFs, and to all other study documents.

**9.2.2 Internal Monitoring**

Data will be captured in Oncore, Moffitt's Clinical Trials Database. The Case Report Forms will be reviewed by Moffitt's Internal Monitors, periodically, approximately every 3 months, throughout the conduct of the trial. The monitoring will include source data verification utilizing research subjects' medical records.

**10 Statistical Considerations****10.1 Study Design/Endpoints**

This is a phase II, single institution, and non-randomized study of patients with untreated CLL/SLL, utilizing a two-stage trial design. The primary endpoint for this trial is the combined complete and partial response rate (at 3 months-the end of cycle 3) to the protocol therapy. We anticipate this trial will have a CR+PR response rate of at least 80%.

A two-stage design is employed for this trial. The null/unacceptable CR+PR response rate is  $\leq 60\%$  while the anticipated true response rate to the protocol treatment is at least 80% for each disease cohort. At the first stage, 26 patients will be accrued to the trial. If 15 or fewer of these patients respond, then the trial will be terminated early and the response rate to the protocol treatment will be deemed unacceptable ( $\leq 60\%$ ). Otherwise, if more than 15 patients respond during the first stage, an additional 19 patients will be enrolled to this trial during stage 2 for a total of 45 patients. If 32 or fewer of these 45 patients respond to the protocol treatment at the end of stage 2, no further investigation of the protocol treatment is considered warranted. On the other hand, if more than 32 patients out of the 45 enrolled patients respond, the protocol treatment will be considered promising. If the true response rate is  $\leq 60\%$ , the probability of ending the trial at stage 1 is 0.48. If, however, the true response rate is at least 80%, then the probability of ending the trial at stage 1 is only 0.01. This two-stage design has an overall alpha level of 0.045 and a power of 0.90.

**10.2 Sample Size/Accrual Rate**

Up to 45 patients will be enrolled into this study. During the interim analysis at the end of stage 1, the patient accrual to the trial will not be suspended while pending the interim analysis results unless the observed objective response rate among those patients whose objective response data are available is below 55%. The accrual rate will be approximately 2-3 patients per month. The entire accrual for this trial should be completed in about 1.5 years.

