#### **STUDY DESIGN:**

This is a phase II, single institution, and non-randomized study of patients with untreated CLL/SLL, utilizing a two-stage trial design. The primary endpoint for this trial is the combined complete and partial response rate (at 3 months, after the end of cycle 3) to the protocol therapy. We anticipate this trial will have a CR+PR response rate of at least 80%.

A two-stage design is employed for this trial. The null/unacceptable CR+PR response rate is  $\leq 60\%$  while the anticipated true response rate to the protocol treatment is at least 80% for each disease cohort. At the first stage, 26 patients will be accrued to the trial. If 15 or fewer of these patients respond, then the trial will be terminated early and the response rate to the protocol treatment will be deemed unacceptable ( $\leq 60\%$ ). Otherwise, if more than 15 patients respond during the first stage, an additional 19 patients will be enrolled to this trial during stage 2 for a total of 45 patients. If 32 or fewer of these 45 patients respond to the protocol treatment at the end of stage 2, no further investigation of the protocol treatment is considered warranted. On the other hand, if more than 32 patients out of the 45 enrolled patients respond, the protocol treatment will be considered promising. If the true response rate is  $\leq 60\%$ , the probability of ending the trial at stage 1 is 0.48. If, however, the true response rate is at least 80%, then the probability of ending the trial at stage 1 is only 0.01. This two-stage design has an overall alpha level of 0.045 and a power of 0.90.

For the purpose of interim analysis at the end of stage 1, the objective response will be measured by the end of 3 months (or end of cycle 3) from the start of the protocol treatment prior to the initiation of the combination of ofatumumab with lenalidomide. The accrual will not be suspended while waiting for the results of the interim analysis unless the observed objective response rate among those patients whose objective response data are available is below 55%.

HiLOG Dosing Schema																										
300 mg	2000 mg doses						2000-mg doses																			
D1	D8	D15	D22	D1	D15	D1	D15	Q 2months																		
Cycle 1			Cycle 2-3			Cycle 4-12																				
▲	▲	▲	▲	▲	▲	▲	▲	Lenalidomide 5-10mg* D1-28 C4-12																		
▲ = HDMP 1000mg/m 																										
↓ = Ofatumumab																										

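### Is the 55% accrual-pause trigger too lax for a stage-1 boundary of 15 responders in 26?

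*Combined protocol and SAP*

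**What the plan says.** The stage-1 rule in Section 10.1 is a count: "At the first stage, 26 patients will be accrued to the trial", and "If 15 or fewer of these patients respond, then the trial will be terminated early". Otherwise, "if more than 15 patients respond during the first stage, an additional 19 patients will be enrolled". The unacceptable rate is 60% or lower and the anticipated rate is at least 80%.

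The pause clause is separate. The synopsis (Section 1, Study Design) says "The accrual will not be suspended while waiting for the results of the interim analysis" and then gives the exception. Section 10.2 repeats it: accrual stays open "unless the observed objective response rate among those patients whose objective response data are available is below 55" per cent. Section 10.2 also gives the expected pace: "The accrual rate will be approximately 2-3 patients per month". Section 1 places the interim response assessment at 3 months, the end of cycle 3.

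The documents give no reason for 55%. They do not say whether the rate is looked at once or as each result arrives.

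**The concern.** The only visible purpose of the pause is to limit enrolment while stage 1 may be failing. One would therefore expect it to trip no later than the boundary it anticipates. Yet 15/26 is 57.7%, and accrual pauses only below 55%. Between the two lies a band in which the observed rate, if it were final, would end the trial while recruitment continues. The sharpest case is 14 of 25 (56.0%): the best attainable result is then 15 of 26, so failure is certain, and the clause still leaves accrual open.

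At stake would be patients enrolled on a regimen that the trial is about to declare unacceptable. With results taking 3 months and 2 to 3 patients a month, that is up to 6 to 9 patients in a failing trial that is never paused.

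**Working it through.** **Inputs.** Section 10.1: 26 patients and boundary 15 at stage 1; 45 patients and boundary 32 overall; rates 0.60 and 0.80. Section 10.2: trigger 55%, accrual 2 to 3 per month. Section 1: response read at 3 months. Hence 3 × 2 = 6 to 3 × 3 = 9 results are pending when the 26th patient enrols, so 26 − 9 = 17 to 26 − 6 = 20 patients are assessed. This assumes that each result is available at 3 months.

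**1. The plan's own figures.** The stage-1 stopping probability is P(X ≤ 15), X ~ Bin(26, p). The probability of a promising result is the sum over x = 16 to 26 of P(X = x) · P(Y ≥ 33 − x), Y ~ Bin(19, p).

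| Quantity | Computed | Stated |
|---|---|---|
| Stop at stage 1, p = 0.60 | 0.4787 | 0.48 |
| Stop at stage 1, p = 0.80 | 0.0079 | 0.01 |
| Alpha | 0.0445 | 0.045 |
| Power | 0.9001 | 0.90 |

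The 55% appears in none of these formulas, so changing it changes none of them.

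**2. Where the two thresholds differ.** For m assessed patients, list the counts x with 0.55 ≤ x/m ≤ 15/26. From m = 17 to 25 there are five: 10/18, 11/20, 12/21, 13/23 and 14/25. At m = 17, 19, 22 and 24 there is none, and the two thresholds give the same decision.

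**3. Have those trials failed?** The chance of still passing is P(Z ≥ 16 − x), Z ~ Bin(26 − m, p).

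| Observed | Needed from pending | p = 0.80 | p = 0.60 |
|---|---|---|---|
| 10/18 | 6 of 8 | 0.80 | 0.32 |
| 11/20 | 5 of 6 | 0.66 | 0.23 |
| 12/21 | 4 of 5 | 0.74 | 0.34 |
| 13/23 | 3 of 3 | 0.51 | 0.22 |
| 14/25 | 2 of 1 | 0 | 0 |

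Four of the five remain open. The exception has one result outstanding.

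**4. One look when the 26th patient enrols.** Share of stage-1 failures that are not paused at p = 0.60, that is P(not paused and X ≤ 15)/0.4787:

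| Assessed | Pause below 55% | Pause at or below 57.7% |
|---|---|---|
| 17 | 0.344 | 0.344 |
| 18 | 0.481 | 0.234 |
| 19 | 0.360 | 0.360 |
| 20 | 0.500 | 0.244 |

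The contrast is large at 18 and 20 and nil at 17 and 19. It depends on which fractions the denominator allows.

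**5. Rechecking with every result up to the 25th.** Carry the distribution of responders forward one patient at a time, removing paths at the first pause; a paused trial stays paused until the 26th result. Assume one enrolment per result. Ranges are over starting counts 17 to 20.

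| Quantity | Below 55% | At or below 57.7% |
|---|---|---|
| Failures never paused, p = 0.60 | 15–20% | 5–6% |
| Mean extra enrolled per failure, p = 0.60 | 1.8–2.3 | 0.8–1.5 |
| Any pause, p = 0.70 | 10–14% | 17–19% |
| Of those pauses, trials that then pass stage 1 | 13–31% | 32–40% |
| Any pause, p = 0.80 | 0.7–1.4% | 1.6–2.2% |
| Of those pauses, trials that then pass stage 1 | 28–60% | 58–68% |

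Compared at the same starting count, the higher trigger saves 0.7 to 1.2 enrolments per failing trial. Multiplied by the 0.479 chance of failing at p = 0.60, that is 0.3 to 0.6 per trial.

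**The case for a change.** The strongest argument for changing the trigger is that it would cost almost nothing: one number in two places, with both decision boundaries untouched. At the anticipated 80% a pause would remain rare, and a pause is not a stop. Continued enrolment at 14/25 cannot be defended by any hope of passing, and the protocol offers no argument for 55%.

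Part of this stands. The 14/25 case is real, though with one result pending it exposes about one further patient. The checking schedule is unstated and it matters: under the 55% rule the unpaused share of failures at a true 60% is 34–50% with a single look and 15–20% with rechecking. A sentence on timing would be a useful clarification.

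What does not stand is the premise that the trigger ought to equal 15/26. A cut-off for 26 complete results is not the natural threshold for 17 or 20; the chance of still passing would be a better guide, and by that measure most of the band is undecided. A lower trigger tolerates noise in immature data, at the price of pausing some failing trials later or not at all. A higher one reverses that exchange.

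The 3-month input is also soft. Footnote 13 of the assessment schedule in Section 2 allows up to 14 days after the cycle 3 marrow for results, which at 2 to 3 patients a month adds 1 to 1.5 pending patients. That could increase the exposure somewhat, but it does not turn a pause rule into a decision rule.

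**Conclusion.** The concern does not hold. The arithmetic gap between 55% and 57.7% exists, but the two figures do different jobs: one decides stage 1 on 26 complete results, the other decides whether to recruit while results are outstanding. They do not contradict each other. Alpha, power, the stage-1 decision and the trial's conclusion are the same under either trigger.

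The practical effect at a true 60%, with 17 to 20 patients assessed at the 26th enrolment and rechecking at each result, is 0.7 to 1.2 enrolments per failing trial and 0.3 to 0.6 per trial. With a single look it is nil at 17 or 19 assessed. Against that, at a true 70% the chance of a pause rises from 10–14% to 17–19%, and a larger share of those pauses falls on trials that would have passed. Reasonable statisticians could choose either threshold. The unstated checking schedule is a missing detail, not an error in the design.

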**10.3 Stratification Factors**

There are no stratification factors planned for this study.

**10.4 Data Analysis, Reporting and Exclusions Regarding Efficacy Endpoints**

The objective response (CR+PR) rate will be summarized using both a point estimate and its exact confidence interval based on the binomial distribution.

Progression-free survival (PFS), defined as the time from study entry to disease progression, relapse or death due to any cause, whichever is earlier, will be summarized with the Kaplan-Meier curve. Confidence intervals for the median and survival rates at different time points will be constructed if needed. The other secondary endpoint, overall survival (OS), will be analyzed similarly. Both of these two secondary endpoints will be reported descriptively.

The intent-to-treat approach will be used for data analysis of this trial. That means all patients who receive at least one dose of the protocol treatment will be included in the interim and final data analyses. Patients who are lost to follow-up or drop out of study prior to their scheduled response evaluation time due to any reason will be treated as non-responders for response determination and censored for time-to-event type of endpoints at the time of their last assessment/follow-up if no relevant event has occurred by then. A secondary analysis that includes only all eligible patients may be conducted in addition to the primary analysis described above at the discretion of the trial PI and study biostatistician. Other subanalyses may also be considered on the basis of a subset of patients, excluding those for whom major protocol deviations have been identified (e.g., early discontinuation of treatment, major protocol violations, etc.). However, these Amendment 5 Dated 03/02/2016

---

subanalyses may not serve as the basis for drawing conclusions concerning treatment efficacy, and the reasons for excluding patients from the analysis should be clearly reported.

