## 2 Schedule of Study Assessments \*

Procedure	All visits/assessments may be scheduled $\pm$ 3 business days										
	Screening  <math>\leq</math> 28 days from Baseline (First day drug administration)	Cycle 1	Cycles 2 - 3	Cycle 4 				Cycles 5-12	Lenalidomide Maintenance Therapy	Discontinuation From Protocol Therapy 	Follow- Up Phase
	Days 1, 8, 15, and 22	Days 1, and 15	Day 1	Day 3 or 4 at investigator discretion	Day 8	Day 15	Day 22	Day 1 and 15			
Study drug administration **		X	X	X					X	X	
Record prior medications, treatments	X										
Record prior anti-cancer therapies	X										
Physical examination, vital signs, weight	X	X 	X 	X 					X 		
ECOG performance status	X	X 	X 	X 					X 		
ECG	X										
Assess lymphadenopathy, spleen / liver 		X 	X 	X 		X 	X 		X 		
Peripheral blood for , ZAP 70, $\beta$ -2 microglobulin, and IgHV mutational status 	X										
Research samples 	X			X							
Baseline lesion assessment	X			X							
Bone marrow 	X			X					X	X	X 
CT of the neck, chest, abdomen & pelvis 	X			X					X		X 
Hematology 	X	X	X	X 		X 	X 	X 	X 	X 	
Serum chemistry 	X	X	X	X 	X 	X 	X 	X 	X 	X 	
Hepatitis B and C serology, HBV DNA PCR 	X 										
Pregnancy testing 	X			X		X	X	X	X		
Register patient into REMS® program	X										

Prescribe lenalidomide via REMS 				X				X			
Record adverse events 		X	X	X				X	X 		
Record concomitant therapies/procedures		X	X	X				X			
Obtain Follow-Up anti-cancer treatments											X
Obtain Follow-Up survival information											X

\* An unscheduled visit can occur at any time during the study. Source must be maintained for these unscheduled visits. The date for the visit and any data generated must be recorded on the appropriate CRF. Source documents for these unscheduled visits must also be maintained.

\*\* See Table 1 for detailed study drug administration schedule.

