 Physical examination of lymphadenopathy, the spleen and liver will be performed on Days 1 and 15 of Cycle 1 to access for tumor flare reaction, and on Day 1 of subsequent cycles to assess response.

 Peripheral blood for ZAP 70 IgVH mutational status, beta-2 microglobulin analyses will be done only at screening. If ZAP 70, IgVH and beta-2 microglobulin was performed within 6 months of screening date, it is not necessary to repeat at screening. Research samples for storage will be drawn during screening, day 1 of cycle 4, day 1 of Maintenance Therapy or discontinuation from protocol therapy if earlier than the end of cycle 12.

 Bone marrow studies will be performed for all subjects at baseline, at the end of cycle 3 (day 21-28 prior to cycle 4), after completion of cycle 12 and every 6 months afterwards during lenalidomide maintenance therapy for two years. Bone marrow studies at any other time point will be performed at the physician's discretion.

 CT of the neck, chest, abdomen & pelvis will be performed at screening, for response assessment at the end of cycle 3 (day 21-28 prior to cycle 4), after the end of cycle 12 (7-10 days after discontinuation of lenalidomide) and every 6 months afterwards during lenalidomide maintenance therapy for two years. After any other time point, CT scans will be performed at the physician's discretion.

 Hematology – CBC with differential WBC and platelet counts. Hematology profiles are required weekly during Cycle 4 (which corresponds to Cycle 1 of lenalidomide-containing therapy), and during any cycle in which the dose of lenalidomide is escalated or re-escalated. For subjects who are on a stable lenalidomide dose (without dose escalation or interruption of the planned dosing schedule) for  $\geq 1$  cycle of treatment, hematology profiles are required on Days 1 and 15 of the cycle.

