 Cycle 4 may begin up to 14 days after cycle 3 bone marrow biopsy to allow for results of response assessments to be available.

 CBC and CMP only every 4 weeks. See Section 5.8. Any grade 3 or 4 cytopenia will be recorded as an adverse event during Maintenance Therapy. No other adverse events will be recorded during Maintenance Therapy

 Upon discontinuation of study therapy, any diagnostic testing will be at the discretion of the physician.

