#### **4.1.2 Secondary study objective**

To collect preliminary efficacy data on:

- Progression/relapse free survival.
- Overall survival.

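### Does the lack of a stated PFS censoring date after the response evaluation, with scheduled scans only on maintenance, undermine the PFS result?

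*Combined protocol and SAP*

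**What the plan says.** Section 10.4 defines PFS from study entry to progression, relapse or death from any cause, summarises it by Kaplan-Meier, and reports it and OS descriptively. The subject of its only censoring sentence is "Patients who are lost to follow-up or drop out of study prior to their scheduled response evaluation time". They count as non-responders and are "censored for time-to-event type of endpoints at the time of their last assessment/follow-up if no relevant event has occurred by then".

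Disease assessment after cycle 12 is set out elsewhere:

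- Section 2, footnotes 3 and 4: marrow and CT after cycle 12 for everyone, then "every 6 months afterwards during lenalidomide maintenance therapy for two years". Footnote 4 adds: "After any other time point, CT scans will be performed at the physician's discretion". Section 5.8 agrees.
- Section 2, footnote 15: "Upon discontinuation of study therapy, any diagnostic testing will be at the discretion of the physician".
- Section 2, follow-up rows: "Obtain Follow-Up anti-cancer treatments" and "Obtain Follow-Up survival information". The marrow and CT rows also appear to carry marks in the follow-up column, tied to footnotes 3 and 4.
- Section 5.4: patients who complete 12 cycles without progression and do not take maintenance are contacted every six months, and that follow-up ends at progression, study closure, withdrawal or death.
- Section 5.9: early stoppers have the discontinuation assessments and then enter follow-up; no interval is given.

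Section 4.1.2 introduces PFS and OS with the words "To collect preliminary efficacy data on".

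**The concern.** Patients are observed on two schedules after cycle 12. On maintenance there are dated scans every six months for two years. Off maintenance there are contacts described as being for survival, with no required disease assessment. Section 10.4 does not say on what date an event-free patient is censored for PFS once the response evaluation has passed. Its phrase joins assessment and follow-up, and these can be different dates.

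The two readings err in opposite directions. If event-free patients are censored at last contact and some progressions never come to light, PFS is too high. If they are censored at the last scheduled scan while later progressions still count as events, they leave the risk set early but the events stay, and PFS is too low. The choice could be made after the data are seen. PFS is one of only two secondary endpoints, so a marked distortion would matter to anyone using the curve to plan a later trial.

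**Working it through.** **What the plan calculates.** Its only design calculation concerns response at the end of cycle 3: 26 then 45 patients, boundaries 15 and 32. Exact two-stage binomial sums give power 0.9001 at 80% and alpha 0.0445 at 60%, with early-stopping probabilities 0.479 at 60% and 0.008 at 80%. The plan states 0.90, 0.045, 0.48 and 0.01, so its figures are reproduced. None of them depends on PFS, for which the plan gives no figure.

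**Inputs from the plan.** Assessments at the end of cycle 3 (84 days, 2.76 months) and of cycle 12 (336 days, 11.04 months); then four six-monthly scans on maintenance (last at 35.04 months) or six-monthly contacts off it; N = 45.

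**Assumptions not in the plan.** Exponential PFS with median 36 months; 50% on maintenance; 10% of events are deaths; 80-100% of off-maintenance progressions surface at the next contact; potential follow-up uniform over 36-54 months.

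**True values.** S(t) = 2^(-t/36), so S(24) = 0.63 and S(36) = 0.50.

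**Simulated Kaplan-Meier estimates** (200,000 or more patients per cell):

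| Censoring of event-free patients | Surfacing | 24 months | 36 months |
|---|---|---|---|
| Last contact | 100% | 0.640 | 0.508 |
| Last contact | 80% | 0.656 | 0.536 |
| Last contact | 0% | 0.715 | 0.643 |
| Last scheduled scan | 100% | 0.577 | 0.389 |
| Last scheduled scan | 80% | 0.585 | 0.404 |
| Dated status at every contact | 100% | 0.642 | 0.509 |

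**Bias at last contact, 80-100% surfacing.** 24 months: 0.640 - 0.630 = 0.010 to 0.656 - 0.630 = 0.026. 36 months: 0.508 - 0.500 = 0.008 to 0.536 - 0.500 = 0.036. Part of this is only the delay from progression to the next visit, which any six-monthly schedule carries.

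**Sampling error.** 1.96 × sqrt(S(1 - S)/45) = 0.141 at S = 0.63 and 0.146 at S = 0.50. The largest of these biases, 0.036, is about a quarter of the half-width (0.036/0.146 = 0.25).

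**Varying the assumptions.** With 30-70% on maintenance and deaths making up 0-20% of events, last contact gives 0.64-0.66 and 0.50-0.55. With a median of 24 months (true 0.50 and 0.35) it gives 0.51-0.53 and 0.37-0.39; with 60 months (true 0.76 and 0.66), 0.77 and 0.67-0.68.

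**Would a required, dated disease status help?** Recorded at every contact, with all progressions surfacing, it gives 0.642 and 0.509, the same as last contact. With status recorded at 50% of contacts the 36-month value is 0.495; at 25% it is 0.468, an error of 0.032 in the other direction. If each contact detects only half of progressions, it gives 0.669 and 0.537, no better than last contact at 80% surfacing.

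**The case for a change.** The strongest case for a change is that two readings of one undefined date give 36-month estimates 0.12-0.13 apart on the same data (0.508 - 0.389 = 0.119; 0.536 - 0.404 = 0.132). That is close to the whole confidence half-width, and it is systematic rather than random. Writing the rule down would cost a sentence and one data item, with no extra scans. Exit assessments alone do not cure the understatement: with 20% stopping between cycles 3 and 12, last-scan censoring gives 0.350-0.365 at 36 months. And if progressions go unrecorded in numbers, last contact overstates PFS. Among off-maintenance patients alone, counting from cycle 12 with a 36-month median, recording 75% of progressions gives 0.72 at 24 months against a true 0.63, and recording 50% gives 0.81.

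The arithmetic stands; its force is limited. The low values require event-free patients to be censored at the last scheduled scan while later progressions count. Section 10.4 does not say this: its wording covers follow-up as well as assessment, and a discretionary examination is also an assessment. The high values require many progressions to stay hidden, which sits badly with contacts that stop at progression and with the collection of later anti-cancer treatment. A censoring sentence cannot recover a progression nobody recorded.

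It also stands that Section 10.4 gives no explicit date for patients event-free after the response evaluation, that Section 5.9 gives early stoppers no interval, and that footnote 15 sits awkwardly with the discontinuation assessments in Sections 5.4 and 5.9. Sections 5.5, 5.5.3.3 and 5.8 also differ on who may continue lenalidomide after cycle 12. Those passages should be reconciled as separate editorial matters; they do not turn on the censoring date.

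**Conclusion.** The gap is real but is missing detail that an analyst would fill sensibly. It would go too far to say that off-maintenance PFS rests on undated status: there is a post-cycle-12 assessment for all completers, then dated six-monthly contacts that end at progression, with later treatment recorded. Read in the ordinary way, with contacts until progression and censoring at last contact, the plan gives an illustrative bias of about 0.01-0.03 at 24 months and 0.01-0.04 at 36 months, against a half-width of 0.14-0.15. A required status item gives the same estimate when complete and can do worse when sparse, so it brings no material gain.

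This rests on the assumed 36-month median, an even split on maintenance, follow-up of 36-54 months and 80-100% surfacing; the documents fix none of these. It would weaken if most off-maintenance progressions went unrecorded. Even then the damage would be confined to a preliminary, descriptive secondary endpoint with no decision rule. The response decision at the end of cycle 3, its alpha and its power are unaffected. Stating the PFS and OS censoring dates in Section 10.4 would be a reasonable courtesy to readers, but the trial's conclusions do not depend on it.
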